6.2. Background Characteristics

6.2.1. Subject Disposition

The number and percentage of subjects in the following categories (analysis sets defined in Section 5) will be summarized as defined in [Section 6.1](#) based on Randomization Set:

- Randomization Set
- Full Analysis Set
- Modified Intent-to-Treat Set
- Per-protocol Set
- Solicited Safety Set
- Safety Set

The denominators of the percentages will be based on subjects in the Randomization Set. The number of subjects in the following categories will be summarized based on subjects screened:

- Number of subjects screened
- Number and percentage of screen failure subjects and the reason for screen failure

The percentage of subjects who screen failed will be based on the number of subjects screened. The reason for screen failure will be based on the number of subjects who screen failed.

The number and percentage of randomized subjects will be summarized by site and by stratification factor at randomization (i.e. ≥ 18 and < 65 years and not at risk, ≥ 18 and < 65 years and at risk, or ≥ 65 years) separately based on the Randomization Set.

The number and percentage of subjects in each of the following disposition categories will be summarized based on the Randomization Set:

- Received each dose of IP
- Prematurely discontinued before receiving the second dose of IP and the reason for discontinuation
- Completed study
- Prematurely discontinued the study and the reason for discontinuation

Subjects with any inclusion and exclusion criteria violation will be provided in a listing.

6.2.2. Demographics and Baseline Characteristics

Descriptive statistics will be calculated for the following continuous demographic and baseline characteristics: age (years), weight (kg), height (cm), body mass index (BMI) (kg/m^2). The number and percentage of subjects will be provided for categorical variables such as age group, sex, race, ethnicity, randomization stratum under which the subject was randomized, and risk factors at Screening (have at least one of the following):

- Chronic lung disease (e.g., emphysema and chronic bronchitis, idiopathic pulmonary fibrosis, and cystic fibrosis) or moderate to severe asthma
- Significant cardiac disease (e.g., heart failure, coronary artery disease, congenital heart disease, cardiomyopathies, and pulmonary hypertension)
- Severe obesity (body mass index ≥ 40 kg/m²)
- Diabetes (Type 1, Type 2 or gestational)
- Liver disease
- Human Immunodeficiency Virus (HIV) infection

The summaries will be provided separately based on the FAS, Safety Set, mITT Set and PP Set.

6.2.3. Medical History

Medical history data will be coded by system organ class (SOC) and preferred term (PT) using the Medical Dictionary for Regulatory Activities (MedDRA).

The number and percentage of participants with any medical history will be summarized by SOC and PT based on Safety Set. A participant will be counted only once for multiple events within each SOC and PT. SOC will be displayed in internationally agreed order. PT will be displayed in descending order of frequency of mRNA-1273 and then alphabetically within SOC.

6.2.4. Prior and Concomitant Medications

Prior and concomitant medications and non-study vaccinations will be coded using the WHO drug dictionary (WHODD). The summary of concomitant medications will be based on the Safety set. Categorization of prior, concomitant, and post medications is summarized in [Appendix C Table 11](#) and will be summarized.

The number and percentage of subjects who continued or newly received concomitant medications and non-study vaccinations will be summarized by treatment group by PT in descending frequency in the mRNA-1273 group:

- Any concomitant medications
- Any non-study vaccine
- Antipyretics or analgesics medication, summaries will be provided for during the 7-day follow-up period of each injection, and during the 28 days follow-up period after each injection (for 1st injection, up to 2nd injection or 28 days after the 1st injection)

6.2.5. Study Exposure

Number and percentage of subjects receiving 1st and 2nd injections will be summarized by treatment arm, the timing of the 2nd injection will be summarized by arm.

6.2.6. Major Protocol Deviations

Major protocol deviations are a subset of protocol deviations that may significantly impact the completeness, accuracy, or reliability of the study data or that may significantly affect a subject's rights, safety, or well-being. Major protocol deviations rules will be developed and finalized before database lock.

The number and percentage of the subjects with each major protocol deviation type will be provided by treatment group as defined in [Section 6.1](#) based on the Randomization Set.

Select major protocol deviations impact critical or key study data, and subjects with such deviations will be excluded from the Per-Protocol Set for efficacy analyses, such major protocol deviations will be determined and documented by Sponsor prior to DBL and unblinding. Reasons of exclusion from Per-Protocol Set for efficacy will be summarized.

6.3. Efficacy Analysis

The PP Set is the primary analysis population for efficacy analyses, unless otherwise specified. PP Set, mITT Set, and FAS will be used for efficacy analyses and subjects will be included in the treatment group which they are randomized to.

Surveillance for COVID-19 will be performed starting after enrollment through the end of the study.

An Adjudication Committee (AC) blinded to treatment assignment will review potential cases and adjudicate COVID-19, the primary efficacy endpoint, and severe COVID-19. Adjudication committee assessments have been used in the two efficacy analyses that have been performed to date: the first interim analysis based on data snapshot occurred on 11-Nov-2020, the primary analysis based on data snapshot occurred on 25-Nov (please refer to Section 6.4.2). Adjudication committee assessments will be used in the final efficacy analysis of the blinded data (Section 6.4.3).

Baseline SARS-CoV-2 status is described in Section 6.1. Baseline SARS-CoV-2 status, RT-PCR test results at baseline, serology status at baseline (bAb specific to SARS-CoV-2 nucleocapsid [NP], as measured by Roche Elecsys Anti-SARS-CoV-2 assay) will be summarized by treatment group.

The mITT and PP Sets will only include participants with baseline negative SARS-CoV-2 status.

RT-PCR test results, and bAb specific to SARS-CoV-2 NP will be summarized by visit.

6.3.1. Analysis of the Primary Efficacy Endpoint

6.3.1.1. Primary Efficacy Endpoint Definition/Derivation

The primary efficacy objective is the VE of mRNA-1273 to prevent occurrence of COVID-19 starting 14 days after the second dose of IP. COVID-19 is defined as symptomatic disease based on the criteria specified in [Section 8.1.1](#) of the protocol. Cases

are defined as participants meeting clinical criteria based both on symptoms for COVID-19 and positive RT-PCR test results.

Subjects reporting COVID-19 symptoms, as defined in Section 8.1.2 of the protocol, will be asked to use an eDiary to report COVID-19 symptoms, and an Illness Visit will be scheduled to collect an NP swab if COVID-19 symptoms are reported (refer to Section 8.1.2 of the protocol).

For the primary efficacy endpoint, a COVID-19 case will be identified as a positive post-baseline RT-PCR test result that is prompted by symptom(s), together with eligible symptoms, i.e. a positive PCR result of the eligible symptoms summarized below in Table 1.

An independent Adjudication Committee (AC) blinded to treatment assignments will review potential cases and adjudicate COVID-19 and severe COVID-19 events and the date of COVID-19 and severe COVID-19.

Two sets of COVID-19 will be provided:

- Based on Adjudication Committee assessments
- Based on eligible COVID-19 symptoms (at least 2 systemic symptoms or 1 respiratory symptom) and positive RT-PCR.

Table 1: Derivation for COVID-19 (primary efficacy endpoint)

	COVID-19
Post-baseline PCR results at illness visits prompted by symptom(s)	Positive, AND
Systemic Symptoms	at least TWO of the following systemic symptoms : Fever ($\geq 38^{\circ}\text{C}$), chills, myalgia, headache, sore throat, new olfactory and taste disorder(s); OR

Respiratory symptoms	at least ONE of the following respiratory signs/symptoms: cough, shortness of breath or difficulty breathing, OR clinical or radiographical evidence of pneumonia;
----------------------	--

The date of documented COVID-19 (case) will be the later date of ([2 eligible systemic symptoms reported, or 1 eligible respiratory symptom reported] and, [date of positive PCR test]). Specifically, the date of documented COVID-19 will be the later date of the following two dates (date of positive PCR test, and the date of eligible symptom(s)), and the two dates should be within 14 days of each other.

- Date of positive PCR test,
- Date of eligible symptom(s), defined as earliest of
 - Respiratory symptom: earliest date of an eligible respiratory symptom is reported
 - Systemic symptoms: earliest date of the 2nd eligible systemic symptom is reported

The time to the first occurrence of COVID-19 will be calculated as:

Time to the 1st occurrence of COVID-19 = Date of documented COVID-19 – Date of randomization +1.

In the primary analysis approach for the primary efficacy endpoint, cases will be counted starting 14 days after the 2nd injection, i.e. date of documented COVID-19 – Date of the 2nd injection \geq 14 (starting 14 days after the 2nd injection).

In the primary analysis approach for the primary efficacy endpoint, the first occurrence of COVID-19 starting 14 days after the 2nd injection will be considered event. In the various sensitivity analyses planned to examine the onset of COVID-19, the censoring rules of cases are outlined in Table 2 below.

In this study, during the blinded phase, there is a scheduled NP swab test at the Day 29 visit prior to the 2nd injection of IP; and blood samples are collected with bAb against SARS-CoV-2 nucleocapsid (NP) tested at months 1, 2, 7, 13 and 25. At IA1 and the Primary Analysis of efficacy, RT-PCR results at scheduled pre-dose 2 (Day 29) and bAb against SARS-CoV-2 nucleocapsid at Day 29 were not considered in the derivation of COVID-19.

At the final blinded efficacy analysis, subjects with early infection, as detected by positive RT-PCR at scheduled pre-dose 2 visit (Day 29), or positive bAb against SARS-CoV-2 NP in blood samples at the scheduled visits, are censored at the time of early infection. If a participant had eligible symptom(s) within 14 days of positive RT-PCR at scheduled pre-dose 2 visit, the participant is considered to be a case for COVID-19.

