4. Participants with symptoms of COVID-19 will be asked to return within 72 hours or as soon as possible to the study site for an unscheduled visit, to include an NP swab sample (for RT-PCR testing) and other clinical evaluations. If a study site visit is not possible, a home visit may be arranged to collect the NP swab sample and conduct clinical evaluations. If a home visit is not possible, the participant will be asked to submit a saliva sample to the study site by a Sponsor-approved method. At this visit, an NP swab and blood sample will be collected to evaluate for the presence of SARS-CoV-2 infection. An additional NP swab sample will be collected to test for the presence of other respiratory pathogens. Additionally, clinical information will be carefully collected to evaluate the severity of the clinical case. It is important to note that some of the symptoms of COVID-19 overlap with solicited systemic ARs that are expected after vaccination with mRNA-1273 (eg, myalgia, headache, fever, and chills). During the first 7 days after vaccination, when these solicited ARs are common, investigators should use their clinical judgement to decide if an NP swab should be collected. The collection of an NP swab prior to the Day 1 and Day 29 vaccination can help ensure that cases of COVID-19 are not overlooked. Any study participant reporting respiratory symptoms during the 7-day period after vaccination should be evaluated for COVID-19.
5. Sample must be collected prior to dosing on days of injection (Day 1 and Day 29).
6. The participant will record entries in the eDiary approximately 30 minutes after dosing while at the study site, with instruction provided by study staff. Study participants will continue to record in the eDiary each day after they leave the study site, preferably in the evening, on the day of dosing and for 6 days following. Any solicited AR that is ongoing beyond Day 7 will be reported until resolution. Adverse reactions recorded in eDiaries beyond Day 7 should be reviewed either via phone call or at the following study visit. Participants will be given thermometers to record their temperatures and rulers to measure any injection site reactions.

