6.3.1.3. Sensitivity Analyses with COVID-19 Cases Counted Starting at Various Timepoints

Sensitivity analyses will be performed with COVID-19 cases counted starting at various timepoints as below using the PP Set. The censoring rules for analyses of the primary endpoint are summarized in Table 2.

- immediately after the second injection of IP
- 14 days after the first injection of IP (also as primary analysis approach for the secondary efficacy objective: To evaluate the efficacy of mRNA-1273 to prevent COVID-19 after the first dose of IP.)
- immediately after the first injection of IP
- immediately after randomization

If <10% of the COVID-19 cases received the first injection after the day the subject was randomized, sensitivity analysis with COVID-19 cases counted starting after the first injection of IP may not be performed separately, as it would be very similar to the sensitivity analysis with COVID-19 cases counted starting from randomization.

Table 2: Censoring Rules for COVID-19

Situation	Primary Efficacy Approach (cases ≥ 14 days after Dose 2)	Sensitivity Analyses			
		Cases starting after Dose 2	Cases ≥ 14 days after Dose 1	Cases starting after Dose 1*	Cases starting after randomization
Early case from randomization up to first injection	Censored at date of case	Censored at date of case	Censored at date of case	Censored at date of case	Event
Early case from Dose 1 up to ($<$) 14 days after Dose 1	Censored at date of case	Censored at date of case	Censored at date of case	Event	Event
Early case from ≥ 14 days after Dose 1 up to ($<$) Dose 2	Censored at date of case	Censored at date of case	Event	Event	Event
Early case from Dose 2 up to ($<$) 14 days after Dose 2	Censored at date of case	Event	Event	Event	Event
Case ≥ 14 days after Dose 2	Event	Event	Event	Event	Event
Early discontinuation or death without documentation of COVID-19	Censored at date of discontinuation/death				

Situation	Primary Efficacy Approach (cases \geq14 days after Dose 2)	Sensitivity Analyses			
		Cases starting after Dose 2	Cases \geq14 days after Dose 1	Cases starting after Dose 1*	Cases starting after randomization
Early infection as detected by: positive RT-PCR at scheduled visit (pre-dose 2), or, positive bAb against SARS-CoV-2 NP in blood samples at the scheduled visits	Censored at date of early infection				

* To be performed if there are \geq 10% of total cases with Dose 1 date > randomization date

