As serum samples were taken at scheduled visits (e.g. Day 29[month 1], Day 57[month 2]), sensitivity analyses with cases counted starting after 2nd dose, 14 days after first dose, after first dose and after randomization are the same. Only one set of sensitivity analysis with cases counted starting from randomization will be provided. In this sensitivity analysis, asymptomatic cases detected by positive RT-PCR result at scheduled pre-dose 2 visit (Day 29), or seroconversion at timepoints with scheduled visits will be considered. Sensitivity analysis using the mITT Set with cases counted starting from 14 days after the second injection, and from randomization will also be performed.

Stratified Cox PH model may also be used.

For the secondary efficacy objective: VE to prevent COVID-19 after the first injection of IP

This endpoint will be analyzed as a sensitivity analysis of the primary efficacy endpoint with cases counted starting 14 days (≥ 14 days) after the first injection of IP as described in [Section 6.3.1](#).

For the secondary efficacy objective: VE to prevent COVID-19 disease regardless of prior SARS-CoV-2 infection

This endpoint will be analyzed using the FAS. The same methods described above for the primary efficacy endpoint will be applied with cases counted starting 14 days after the second injection of IP.

Sensitivity analyses with cases counted starting immediately after the second injection, 14 days after the first injection, and after randomization will also be performed. In sensitivity analysis with cases counted starting after the second

injection, subjects who received only the first injection and is a case will be censored at the time of COVID-19.

The VE will also be estimated with 1- ratio of incidence rates with the 95% CI using the exact method conditional upon the total number of cases adjusting for person-time.

In addition, an exploratory analysis with the same Cox model will be carried out in the subgroup of FAS whose baseline SARS-CoV-2 status is positive with cases counted starting from randomization to assess the VE in those with positive baseline SARS-CoV-2 status, at baseline, if sample size permits. Such analysis in the subgroup of FAS whose baseline SARS-CoV-2 status is negative with cases counted starting from randomization is the same as the sensitivity analysis of COVID-19 starting from randomization in mITT.

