6.5. Multiplicity Adjustments

The overall type I error rate for this study is controlled at 2.5% (one-sided). The overall Type I error rate for the primary efficacy endpoint at the IAs and the primary analysis is strictly controlled at 2.5% (1-sided) based on the Lan-DeMets O'Brien-Fleming approximation spending function. The primary efficacy endpoint will be considered statistically significant after consideration of the strategy for controlling the Type I error as described in Section 6.4 Interim Analyses. Statistical significance of the primary efficacy endpoint can be achieved at either one of the interim analyses or at the primary analysis. A sequential/hierarchical testing procedure will be used to control type 1 error rate over the primary efficacy endpoint and the secondary efficacy endpoints. Secondary efficacy endpoints will only be tested when the primary efficacy endpoint achieves statistical significance.

If the primary efficacy endpoint achieves statistical significance at either one of the interim analyses or at the primary analysis, a fixed-sequence statistical strategy will be used to test the following secondary efficacy endpoints in a pre-defined order:

1. secondary efficacy endpoint: COVID-19 regardless of evidence of prior SARS -CoV-2 infection at the same analysis (through the same follow-up period)

2. secondary efficacy endpoint: infection regardless of symptomatology or severity at the same analysis (through the same follow-up period)
3. secondary efficacy endpoint: severe COVID-19 at the analysis with ≥ 20 cases, otherwise, to test at the end of the study

[figure not shown]
If the primary efficacy endpoint achieves statistical significance at either one of the interim analyses or at the primary analysis, sequential tests of the above 3 secondary efficacy endpoints will be performed at one-sided Type I error rate of 0.025.

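### Read literally, the nucleocapsid-antibody censoring rule takes participants who were seropositive at baseline and still positive at Day 29 out of the final blinded FAS estimate of VE regardless of prior infection before any case can count

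*SAP*

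**What the plan says.** SAP Part A section 6.3.1.1 notes that blood is drawn with "bAb against SARS-CoV-2 nucleocapsid (NP) tested at months 1, 2, 7, 13 and 25"; month 1 is the Day 29 visit. For the final blinded analysis it then states that subjects with early infection, found by a positive scheduled pre-Dose-2 swab or by "positive bAb against SARS-CoV-2 NP in blood samples at the scheduled visits, are censored at the time of early infection". Table 2 in section 6.3.1.3 has a matching row: "Early infection as detected by: positive RT-PCR at scheduled visit (pre-dose 2), or, positive bAb against SARS-CoV-2 NP in blood samples". Neither place makes the rule depend on baseline status.

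For the two earlier efficacy analyses, section 6.3.1.1 says that the Day 29 swab and "bAb against SARS-CoV-2 nucleocapsid at Day 29 were not considered in the derivation of COVID-19".

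For COVID-19 regardless of prior infection, section 6.3.2.2 says: "This endpoint will be analyzed using the FAS. The same methods described above for the primary efficacy endpoint will be applied", with counting from 14 days after Dose 2. It adds FAS sensitivity analyses counted from Dose 2, from 14 days after Dose 1 and from randomization. It also plans an exploratory Cox analysis in the "subgroup of FAS whose baseline SARS-CoV-2 status is positive with cases counted starting from randomization". Section 6.5 puts "secondary efficacy endpoint: COVID-19 regardless of evidence of prior" infection first among the secondary endpoints in the fixed sequence.

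On sample timing, the protocol (Appendix 1, Table 16, footnote 5) says: "Sample must be collected prior to dosing on days of injection (Day 1 and Day 29".

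**The concern.** Section 6.3 states that the mITT and PP Sets hold only baseline-negative participants. In those sets a positive nucleocapsid antibody at a scheduled visit does mean a new infection, and the rule does no harm. The FAS also contains people who were already antibody-positive on Day 1. For them a positive Day 29 result may only be the baseline antibody persisting, yet the rule as worded ends their follow-up there.

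This endpoint exists to bring people with prior infection into the efficacy estimate. If they are censored before the counting window opens, the estimate carries a label that its content does not support. The baseline-positive subgroup would also describe only the interval between the two doses, and so could say nothing about a two-dose schedule.

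**Working it through.** The documents give no count, person-time or power for baseline-positive participants, so there is no stated figure to reproduce. The check is one of timing.

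**Inputs**
- Randomization and Dose 1 are on Day 1.
- The Day 29 visit has a window of -3/+7 days (protocol Table 16), that is Day 26 to 36. Dose 2 is taken to be given at that visit, after the blood draw.
- The main analysis counts cases from Dose 2 + 14 days (SAP 6.3.1.1).
- Assumption: a participant who is seropositive at baseline is still positive at the first scheduled post-baseline sample. The documents give no data on persistence.

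**Formula:** countable days = max(0, censoring day − day on which counting starts).

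| Analysis | Counting starts | Censored | Countable days (visit-window range) |
|---|---|---|---|
| FAS main, Dose 2 + 14 | 29 + 14 = Day 43 (40–50) | Day 29 (26–36) | max(0, 29 − 43) = 0 (0–0) |
| FAS, after Dose 2 | Day 29 (26–36) | Day 29 (26–36) | 29 − 29 = 0 (0–0) |
| FAS, 14 days after Dose 1 | 1 + 14 = Day 15 | Day 29 (26–36) | 29 − 15 = 14 (11–21) |
| FAS, from randomization | Day 1 | Day 29 (26–36) | 29 − 1 = 28 (25–35) |
| Baseline-positive subgroup | Day 1 | Day 29 (26–36) | 29 − 1 = 28 (25–35) |

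The zero in the first row does not depend on when the visit falls, because the sample always precedes Dose 2 and counting always starts 14 days after it.

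**Departures from the assumption**
- Day 29 sample missing: the next scheduled sample is at Day 57 (54 to 64). With Dose 2 on Day 29, the main analysis keeps 57 − 43 = 14 days (11 to 21).
- Antibody negative at Day 29 and Day 57, then positive at Day 209: 209 − 43 = 166 days are kept.

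**Share of subgroup follow-up kept.** Suppose blinded follow-up would otherwise have ended at Day 120, 150 or 209 (assumed values). The 28 days are then 28/119 = 24%, 28/149 = 19% or 28/208 = 13% of the available time.

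**Number of people.** The baseline-positive share is not stated. At an assumed 1% to 5% of about 30,000, it would be 300 to 1,500 participants.

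**The case against.** The best counter-argument is that the rule censors subjects with early infection at the time of that infection, and that a persisting baseline antibody is not an infection on study. Protocol section 8.1.1 defines serologic infection as seroconversion in participants seronegative at baseline. SAP section 6.3.2.1.3 does the same for the combined infection endpoint. A plan that includes a VE analysis in baseline-positive participants presumably meant to follow them. This is a plausible account of intent. However, sections 6.3.1.1 and 6.3.1.3 identify early infection by how it is detected, and the detection criterion is a positive antibody. The SAP writes the baseline-negative restriction where it wants it and omits it here. Section 1 also says the SAP prevails where it differs from the protocol.

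A second argument is that Table 2 belongs to a section on the PP Set, extended to mITT, and that the censoring list in section 6.3.1.2 does not mention serology. On that view, applying the same methods to the FAS need not bring the rule along. Against this, section 6.3.2.2 says the baseline-negative part of the FAS, counted from randomization, gives the same analysis as the mITT one. That implies the mITT censoring travels into the FAS. It does not alone prove that the rule reaches baseline-positive participants; that follows from the missing baseline condition. What stands is that the text is ambiguous as well as defective, and that the documents do not show how it was programmed.

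A third argument is that baseline-positive status also covers participants who were swab-positive but seronegative, whom this mechanism need not touch. That is correct. They would add little to the main window, though, because protocol section 7.2 lists detection of the virus in the Day 1 swab among the contraindications to further dosing, so under the protocol they would have no Dose 2.

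**Conclusion.** The point holds for the final blinded analysis. Under the literal rule, a participant who was seropositive at baseline and is still positive at the Day 29 sample contributes no countable time to the main FAS estimate or to the after-Dose-2 sensitivity analysis. The main estimate then largely reduces to a baseline-negative one. This rests on antibody persistence to Day 29, on a Day 29 sample being available and on literal programming. The effect on the VE estimate itself cannot be sized from the documents.

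A reader might infer three stronger things that the documents do not support:
- *That the baseline-positive subgroup is empty.* It counts from randomization, so its follow-up is truncated to roughly the interval between doses. The FAS sensitivity analyses from randomization and from 14 days after Dose 1 also keep some time.
- *That every previously infected participant is lost.* A missing Day 29 sample, loss of antibody, or a swab-positive and seronegative baseline all fall outside the mechanism.
- *That the confirmatory result is affected.* Section 6.5 tests this endpoint at the analysis where the primary endpoint succeeded. Section 6.4.2.1 records that as IA1, and neither IA1 nor the primary analysis used the rule. Later efficacy analyses are described as supportive or supplementary, and the subgroup analysis is labelled exploratory.

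**What to change.** In section 6.3.1.1 and the early-infection row of Table 2, replace the positive-antibody trigger with seroconversion: negative at baseline and first positive at a scheduled post-baseline visit. This matches SAP section 6.3.2.1.3 and protocol section 8.1.1. Add one sentence saying that serology-based early-infection censoring does not apply to participants with positive baseline status in any FAS analysis or subgroup.

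The wording change is two sentences and one condition in the censoring program, and PP and mITT results do not change. The introduction to the SAP for Part B and Part C says that the Part A analyses are considered complete, so the sponsor should first check how the FAS censoring was coded. If baseline-positive participants were exempt, document that. If the literal rule was used, rerun and report again the FAS estimate, its sensitivity analyses and the baseline-positive subgroup. That rerun is the larger cost.
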